2.1.3 Expected Adverse Events Related to the Investigational Product

Based on clinical studies and post-marketing experience of the active control (i.e., BeneFIX), the most serious adverse events are systemic hypersensitivity reactions, including bronchospastic reactions and/or hypotension and anaphylaxis, and the development of high-titer inhibitors necessitating alternative treatments to FIX replacement therapy.

In detail, the most common adverse events observed in clinical studies (> 5%) were headaches, dizziness, nausea, injection site reaction, injection site pain, and skin-related hypersensitivity reactions (e.g., rash, hives). Also, the following post-marketing adverse events have been reported: inadequate FIX recovery, inadequate therapeutic response, inhibitor development, anaphylaxis, angioedema, dyspnea, hypotension, and thrombosis.

Considering the findings from previous studies and the mechanism of study drug, it is expected that the study drug will be associated with similar adverse events to the active control.

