5.1.15 Adverse Events (AEs)

The investigator should collect and review AEs of a subject after administration of the investigational products through interview and/or tests. AEs occurring after the administration of investigational products shall be classified into local, systemic, and other AEs^(10, 13). The adverse events are evaluated using the ruler provided and thermometers at institution for accurate assessment of adverse events.

1) Local AE

All local AEs occurring within 1 hour after the administration of investigational products including pain, tenderness, erythema/redness, urticaria/pruritus, and induration/swelling should be recorded. The severity of the symptoms should also be recorded according to separate AE assessment criteria and the causal relationship with the investigational products should also be evaluated. (Appendix 4. Table – Assessment of Local Adverse Events)

2) Systemic AE

All systemic AEs occurring within 1 hour after the administration of investigational products including fever, fatigue/malaise, chill/pyrexia, , headache, myalgia, arthritis(arthralgia), decreased appetite/loss of appetite, diarrhea, vomiting, constipation, abdominal pain, mucosal skin reaction/rash, vasovagal syncope, dizziness, cough, acute bronchospasm, dyspnea, and hypersensitivity should be recorded according to the AE assessment criteria and the causal relationship with the investigational products should also be evaluated. The severity of the symptoms should also be recorded according to separate AE assessment criteria and the causal relationship with the investigational products should also be evaluated. (Appendix 5. Table – Assessment of Systemic Adverse Events)

3) Other AE

All AEs other than local or systemic AEs occurring after the administration of investigational products should be recorded. The severity of the symptoms should also be recorded according to AE assessment criteria and the causal relationship with the investigational products should also be evaluated.

Adverse events of special interest (AESIs) should be collected and analyzed separately. Following AESIs will be monitored.

- Thrombosis/embolism
- Spontaneous bleeding
- Inhibitor generation/seroconversion
- Anaphylaxis

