8.2 Collection and Documentation of Adverse Events

AEs shall be collected during the clinical study period, from the time of investigational product administration to end of a cohort. Any medical incidences before the administration of the investigational product shall be recorded as current medical history.

AEs shall be reported with details on onset/end date, severity, outcome, action taken to investigational products, causal relationship with investigational products, causal relationship with other drugs, treatment given for AE, and seriousness. When documenting AEs, the investigators should record the overall diagnosis or symptoms using standard medical terms (according to the latest version of the MedDRA).

AEs occurring during the study period shall be followed up until recovery (or stabilization), or until the case is lost to follow up. AEs occurring after the study completion should be reported only when they are serious and causally related to investigational products.

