9.5 Safety Evaluation

9.5.1 Adverse Events

The summary table for the following AE will be presented by each cohort. In the summary table, the number and proportion of subjects to whom following AE occurred, and its 95% confidence interval and the number of following AEs will be estimated.

- Adverse Event
- Adverse Drug Reaction^a
- Serious Adverse Event
- Serious Adverse Drug Reaction^a
- Early Withdrawal due to AE^b
- Adverse Event of Special Interest^c

^a Adverse Drug Reaction: AE including whose 'Causal Relationship with IP' is assessed "Definitely related", "Probably related", "Possibly related", "Unknown"

^b Early Withdrawal due to AE: AE whose 'Reason for discontinuation' of 'Study Conclusion' is

'Occurrence of an AE that leads treatment discontinuation' and 'Action taken to IP' is "Interrupted"
 c Adverse Event of Special Interest: It is Thrombosis/embolism, Spontaneous bleeding, Inhibitor generation/seroconversion, Anaphylaxis and collected in other AE only

Additionally, the summary table for the following local¹/systemic²/other³ AE will be presented by each cohort. In the summary table, the number and proportion of subjects to whom local/systemic/other AE occurred, and its 95% confidence interval and the number of following AEs will be estimated.

- Adverse Event
- Adverse Drug Reaction
- Serious Adverse Event
- Serious Adverse Drug Reaction
- Early Withdrawal due to AE

¹ Local AE: AEs occurring within 1 hour after the administration of investigational products including pain, tenderness, erythema/redness, urticaria/pruritus, and induration/swelling

² Systemic Adverse Event: AEs occurring within 1 hour after the administration of investigational products including fever, fatigue/malaise, chill/pyrexia, , headache, myalgia, arthritis(arthralgia), decreased appetite/loss of appetite, diarrhea, vomiting, constipation, abdominal pain, mucosal skin reaction/rash, vasovagal syncope, dizziness, cough, acute bronchospasm, dyspnea, and hypersensitivity

³ Other Adverse Event: AEs other than local or systemic AEs occurring after the administration of investigational products

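### Protocol 8.2 ends AE collection before the post-study inhibitor check, and SAP 9.5.1 can miss a first-hour anaphylaxis filed as systemic, so the AESI table may run low

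*Combined protocol and SAP*

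**What the plan says.** **Collection window**

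- Protocol 8.2 collects AEs "from the time of investigational product administration to end of a cohort". It adds: "AEs occurring after the study completion should be reported only when they are serious and causally related to investigational products". Note h to the study schedule also stops safety endpoints at the end of each cohort.
- Protocol 8.4.1 extends SAE reporting to 14 days after study completion. The last sentence of 8.4.2 tracks other AEs to 14 days after the last dose.
- Protocol 5.2.6 sets a post-study safety visit 2 weeks (+1 week) after cohort end or premature termination. It includes an AE check and inhibitor, anti-drug antibody and Bethesda samples. Section 1.2.4 gives inhibitor detection as the visit's purpose.

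**AESI definition**

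- Protocol 5.1.15, under its 'Other AE' item, says: "Adverse events of special interest (AESIs) should be collected and analyzed separately". It names thrombosis/embolism, spontaneous bleeding, inhibitor generation/seroconversion and anaphylaxis.
- SAP 9.5.1, footnote c, lists the same events and says where they sit: "Spontaneous bleeding, Inhibitor generation/seroconversion, Anaphylaxis and collected in other AE only".
- SAP 9.5.1, footnote 2, defines systemic events as "AEs occurring within 1 hour after the administration of investigational products including fever", followed by a list that ends with bronchospasm, dyspnea and hypersensitivity. Footnote 3 makes 'other' the remainder: "AEs other than local or systemic AEs occurring after the administration of investigational products".

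**Inhibitor results**

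- SAP 9.5.6 counts a subject as positive after one confirmed positive following injection, and treats any numeric inhibitor value as positive. Protocol 5.1.10 uses more than 0.6 BU with a confirmatory test.

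**The concern.** Inhibitor development and anaphylaxis are two of the four AESIs. Protocol 2.1.3 puts high-titer inhibitors and "systemic hypersensitivity reactions, including bronchospastic reactions and/or hypotension and anaphylaxis" among the most serious events known for the active control, and expects a similar profile for the study drug. A separate AESI analysis is therefore a stated purpose of the safety plan.

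Two features could make that analysis incomplete. The visit designed to find late inhibitors lies outside the window in which 8.2 collects AEs. And if the AESI summary is drawn from a single record class, an event filed in another class drops out of it. In either case the AESI table would be too low and would disagree with other outputs in the same report.

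**Working it through.** The plan gives no figure to reproduce here. The check is date arithmetic, a side-by-side reading, and the effect of one omitted subject.

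**1. When the post-study visit falls.** Inputs are the visit days in protocol 5.2.1 to 5.2.4 and the 14-21 day window in 5.2.6. For completers, days after last dose = (end-of-cohort day - last-dose day) + 14 to 21.

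| Cohort | Last dose | End of cohort | Difference | Post-study visit, days after last dose |
|---|---|---|---|---|
| 1-2 | Day 4 | Day 7 | 3 | 17-24 |
| 3 | Day 4 | Day 9 | 5 | 19-26 |
| 4 | Day 5 | Day 10 | 5 | 19-26 |
| 5 | Day 8 | Day 13 | 5 | 19-26 |

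These are nominal days. Protocol 4.4 gives Cohort 4 only 144 hours of observation (Day 6). On that figure the difference is 6 - 5 = 1 and the visit falls at 15-22 days. After premature termination on a dosing day it falls at 0 + 14 to 21 = 14-21 days.

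**2. Which stated window reaches that visit (completers, table above).**

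- 8.2 and note h close at end of cohort, 14-21 days before the visit.
- 8.4.2 closes 14 days after the last dose: 17 - 14 = 3 to 24 - 14 = 10 days before the visit in Cohorts 1-2, and 19 - 14 = 5 to 26 - 14 = 12 days before it in Cohorts 3-5. After premature termination on a dosing day it can just meet the visit. The sentence closes the SUSAR section and may concern follow-up only.
- 8.4.1 reaches only the first day of the visit window, assuming study completion means end of cohort, and covers only SAEs.
- 5.2.6 checks AEs at the visit. The schedule's AE row also appears to mark it, but that table is broken in the available text, so this is probable rather than certain.

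**3. A late inhibitor judged non-serious.** It lies outside 8.2's collection window. If the study counts as complete, it also fails 8.2's serious-and-related test. The end-of-cohort visits for Cohorts 4 and 5 are headed as end of study, and 5.2.6 says the later visit is not a scheduled one, so that reading is available. SAP 9.5.6 states no end-of-cohort cut-off, so a confirmed positive result would count there.

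**4. A first-hour anaphylaxis.** Footnote c sends it to 'other'. Footnote 2's list is open and includes its usual components, and protocol 5.1.15 tells sites that first-hour "acute bronchospasm, dyspnea, and hypersensitivity should be recorded" as systemic. Once filed as systemic, footnote 3 excludes it from 'other'. It would remain in the overall and systemic tables and in the per-patient listing.

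**5. Size of one omission.** SAP 8.7 specifies exact 95% intervals with the cohort as denominator. For 0/n the upper limit is 1 - 0.025^(1/n). For 1/n the lower limit is 1 - 0.975^(1/n) and the upper limit is the 97.5th percentile of Beta(2, n - 1).

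| n | One subject counted | Subject omitted |
|---|---|---|
| 3 | 1/3 = 33.3% (0.8-90.6%) | 0/3 = 0% (0-70.8%) |
| 5 | 1/5 = 20.0% (0.5-71.6%) | 0/5 = 0% (0-52.2%) |

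This is simply 1/n. It implies nothing about how often such an event would occur.

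**The case against.** **On the window.** The text specific to the visit, 5.2.6, orders an AE check. Protocol 5.1.9 makes any clinically significant abnormal laboratory result after dosing an AE, with no end date, and the schedule groups the antibody and Bethesda tests under laboratory tests. Serious and related events survive 8.2 in any case, and relatedness is a low bar because 8.1 counts any reaction whose relationship cannot be ruled out. All of this stands and narrows the gap, chiefly to an inhibitor judged non-serious. It does not remove it, since 8.2 and note h still tell the site that collection has ended.

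**On placement.** A reader might infer that the SAP has no rule for an event that is both an AESI and systemic. The documents do not support that. Footnote c is itself a placement rule, protocol 5.1.15 lists AESIs under 'Other AE', and neither systemic list names anaphylaxis. Protocol 5.1.15 also asks for event time only for AESIs, which suggests they are identified at collection. SAP 9.5.1 tabulates local and systemic events by reported term but other events by SOC and PT, which fits a symptom checklist beside coded diagnoses. What remains is narrower: the footnotes can still lead a site to file a first-hour anaphylaxis as systemic, and footnote c's class would then not contain it. Whether the case report form prevents this cannot be seen.

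**On agreement between tables.** Exact agreement between the AESI table and SAP 9.5.6 is not a fair benchmark while 9.5.6 counts any numeric value and 5.1.10 uses a threshold with confirmation. That is correct, and the remedy has to address it.

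**Conclusion.** The main point holds: protocol 8.2, note h, 8.4.1, 8.4.2 and 5.2.6 do not give one AE window, and the visit meant to detect inhibitors falls 14-21 days after 8.2 and note h stop collection. The placement point holds only as a secondary, conditional risk.

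Severity is minor. A reader might infer that late inhibitors or early anaphylaxis would vanish from the safety results. They would not: a confirmed late inhibitor stays in the SAP 9.5.6 summary and listing, and a misfiled anaphylaxis stays in the overall and systemic tables. Nor does the SAP discard late events. SAP 9.5.1 sets no onset cut-off and plans a listing of antibody-positive other AEs, so a recorded event would be counted. Only the AESI summaries are exposed, by one subject in 3 to 5 per omission.

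The conclusion assumes that a site follows 8.2 over 5.2.6 and judges the inhibitor non-serious or, for the secondary point, files the anaphylaxis as systemic. No such event or omission is claimed to have occurred.

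**What to change.** 1. In the protocol, reconcile 8.2, note h, 8.4.1 and 8.4.2 with 5.2.6 and the schedule's AE row, so that one stated AE/AESI window includes the post-study safety visit.
2. In SAP 9.5.1, identify AESIs from all local, systemic and other records, using the investigator's AESI identification together with the event term, not the record class. The term alone is not enough: an anaphylaxis entered as hypersensitivity or dyspnea would be missed, and counting every such term would inflate the table.
3. State which inhibitor result counts as an AESI, and reconcile that rule with SAP 9.5.6 (any numeric value) and protocol 5.1.10 (more than 0.6 BU with a confirmatory test). If the rules are to differ, say so, so that a difference between the tables is expected.

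The cost is a small protocol text change, which under 9.2 needs IRB approval and MFDS approval if necessary, plus one SAP derivation and one definition. The visit, its AE check and its inhibitor sample already exist.

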9.5.2 Laboratory Tests

For laboratory test, the descriptive statistics for each cohort will be presented in collected visit. And the change of baseline and end of cohort will be presented.

Additionally, the frequency and percentage of 'Normal/NCS', 'CS' in CD4 count of hematology test at screening will be presented. And the frequency and percentage of 'Normal', 'NCS', 'CS' in serology test at screening will be presented.

Also, 'Normal/NCS', 'CS' changes from baseline to end of cohort in hematology test(except for CD4 count), blood chemistry test, urinalysis and blood coagulation test will be summarized in terms of frequency and percentage by cohort.

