5.1.8 Electrocardiogram

Electrocardiogram is obtained at the time of screening, 1st day of hospitalization, interim visits, 2nd hospitalization, and end of a cohort (as there is no interim visit for Cohort 4 and Cohort 5, this is replaced by the date of the 1st investigational product administration). The actual recording date/time, PR, QRS, QT, corrected QT intervals, and investigator's assessment will be recorded in the CRF. Results are classified into followings: 1) Normal, 2) Abnormal, not clinically significant, or 3) Abnormal, clinically significant.

If a clinically significant abnormal finding in electrocardiogram (e.g., abnormal change in QT interval) is observed, it should be recorded as current medical history (at the time of screening) or an adverse event (after the administration of investigational products) on the CRF.

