7.2.3.5 Laboratory Tests

Descriptive statistics from laboratory tests before and after administration of the investigational products shall be presented in mean (\pm standard deviation), median, minimum, and maximum by cohort. Normal/abnormal changes shall be summarized in terms of frequency and percentage.

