4.2 Final Analysis

The statistical analysis of this study will be performed after all data is collected and database lock is completed.

5. Changes to the Planned Analyses in the Protocol

The PK/PD analysis is described in Protocol but PK/PD analysis will be conducted at the designated central laboratory (HTI). So this document does not include this analysis.

6. Analysis Sets

Safety Analysis Set

All subjects who receive at least one dose of investigational products

7. Protocol Deviations

The additional protocol deviations other than analysis set criteria described in '6. Analysis Sets' are not considered.

8. General Specifications for Statistical Analyses

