8.7 Other Statistical Considerations

The analysis will be carried out according to considerations as follows. If additional considerations on each analysis item is required, the corresponding options will be described in '10.1 Derivation'.

- In Cohort 1, Cohort 2, Cohort 3, 'Baseline' is '1st Hospitalization (Before 1st injection)' visit. And in Cohort 4 and Cohort 5, 'Baseline' is 'Before 1st injection' visit.
- The criteria for converting day to month are as follows: 1month=30days
- When calculating percentage for categorical variables except for 'Analysis Sets' summary, the denominator is the number of subjects in each cohort. Only in case of analysis by type of Medical History/Surgical History/Prior Medication/Concomitant Medication, the denominator is the number of subjects having Medical History/Surgical History/Prior Medication/Concomitant Medication in each cohort.
- The calculating criteria of percentage for 'Analysis Sets' summary will be described in 9.1 Disposition of Subjects'.
- The 95% confidence interval will be estimated by using exact method.

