9.5.3 Physical Examination

'Normal/NCS', 'CS' changes from baseline to end of cohort in physical examination results will be summarized in terms of frequency and percentage by cohort. The subjects with clinically significant results in physical examination will be listed.

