9.5.5 Electrocardiogram

For each electrocardiogram results, the descriptive statistics for each cohort will be presented at each collected visit. And the change of baseline and end of cohort will be presented.

'Normal/NCS', 'CS' changes from baseline to end of cohort in electrocardiogram results will be summarized in terms of frequency and percentage by cohort.

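### The SAP's laboratory and ECG shift tables merge Normal with NCS and compare baseline only with end of cohort, an undeclared departure that leaves NCS abnormalities, above all in TAT, D-dimer and F1+2, without a categorical count

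*Combined protocol and SAP*

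**What the plan says.** **Protocol.** For laboratory tests, section 7.2.3.5 states: "Normal/abnormal changes shall be summarized in terms of frequency and percentage". Section 7.2.3.4 says the same for ECG and 7.2.3.2 for physical examination. All three refer to before and after administration without naming a post-dose time. Section 5.1.8 collects ECGs in three grades: "1) Normal, 2) Abnormal, not clinically significant, or 3) Abnormal, clinically significant". Section 5.1.9 schedules the coagulation panel (including TAT, D-dimer and F1+2) at 6 h after dosing, at the planned visits, and at the interim and end-of-cohort visits. Section 5.1.15 lists thrombosis/embolism as an AESI.

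**SAP.** Section 9.5.2 reads: "Also, 'Normal/NCS', 'CS' changes from baseline to end of cohort in hematology test(except for CD4 count), blood chemistry test, urinalysis and blood coagulation test", to be given as frequency and percentage by cohort. Section 9.5.5 uses the same two categories and two time points for ECG. For physical examination, 9.5.3 again uses Normal/NCS against CS, with "changes from baseline to end of cohort in physical examination results will be summarized in terms of frequency and percentage by cohort". Section 10.2 fixes the merged category for all of these. Section 5, which lists changes from the protocol, names only the transfer of the PK/PD analysis to the central laboratory.

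The SAP uses finer rules elsewhere. Screening serology keeps Normal, NCS and CS apart (9.5.2, 10.2), and one positive inhibitor or antibody result at any time after injection counts as positive (9.5.6).

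**The concern.** Two separate features are at work.

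- **The merge.** A subject who is normal at baseline and abnormal-NCS at end of cohort is tabulated as unchanged. The protocol's normal/abnormal count cannot be recovered from that table.
- **The single post-dose time.** An abnormality of any grade that has resolved by end of cohort cannot enter the shift table.

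The combination bites hardest on the coagulation activation markers. They are the laboratory counterpart of the thrombosis AESI, and the dose rationale (section 1.2.3) cites a link between high FIX concentration and deep vein thrombosis as the reason for limiting Cmax. The NCS label is also an investigator's judgement in an open-label study, so the grade that decides whether a change is counted is set with treatment known.

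**Working it through.** **1. Draws available against draws used.** These are the scheduled post-baseline coagulation draws per subject under protocol 5.2. Only the end-of-cohort draw enters the shift table.

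| Cohort | Post-baseline draws | Total | Not in shift table |
|---|---|---|---|
| 1, 2 | 6, 24, 48, 72 h; 2nd hospitalization; 6, 24, 48, 72 h | 9 | 8 (89%) |
| 3 | 6, 24, 48, 72 h; 2nd hospitalization; 6, 24, 48, 72, 120 h | 10 | 9 (90%) |
| 4 | 5 pre-dose and 5 at 6 h (Visits 2 to 6); Visits 7, 8, 9 | 13 | 12 (92%) |
| 5 | 8 pre-dose (Visits 2 to 9); Visits 10, 11, 12 | 11 | 10 (91%) |

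No 6 h or 24 h draw enters. The counts for Cohorts 4 and 5 rise if the 6 h draws stated in 5.1.9, but not itemised in 5.2, are also taken.

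**2. Where end of cohort lies relative to peak.** The protocol's SC assumptions (Table 1.1, note 3) are Cmax 5.1 IU/dL at 75 IU/kg, Tmax 8 h, half-life 33.8 h and exponential decline from Cmax. First, a check against the plan's own figures, using time to 1 IU/dL = 8 + 33.8 × log2(Cmax):

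- Cmax 5.1: 87.4 h (stated 88)
- Cmax 10.2: 121.2 h (stated 124)
- Cmax 20.4: 155.0 h (stated 156)

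All agree within 3%. The fraction of peak is then 0.5^((t − 8)/33.8):

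- 24 h: 0.72
- 72 h (end of Cohort 2): 0.27
- 120 h (end of Cohorts 3, 4 and 5): 0.10

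For Cohort 1, the protocol's IV figures give 2.5/55 = 4.5% at 72 h. These are fractions of FIX activity. They place the sample in time and do not measure TAT, D-dimer or F1+2, for which the documents give no kinetics.

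**3. ECG.** In Cohorts 1 to 3, ECGs are scheduled at screening, at each hospitalization, at the interim visit and at end of cohort, with none at 6 h or 24 h. In Cohorts 4 and 5, protocol 5.2.3 and 5.2.4 add ECGs at 24 h and 72 h after the last dose, and the shift table does not use them.

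**4. Baseline.** SAP 8.7 states: "In Cohort 1, Cohort 2, Cohort 3, 'Baseline' is '1st Hospitalization (Before 1st injection)' visit". The one shift in Cohort 1 therefore spans BeneFIX and then ISU304, and in Cohorts 2 and 3 it spans the IV and then the SC dose. It cannot be attributed to one administration.

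**5. What other outputs show.**

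| Finding | Reported elsewhere? |
|---|---|
| CS laboratory, ECG or physical finding after dosing | Yes, recorded as an AE (protocol 5.1.6, 5.1.8, 5.1.9) and tabulated (SAP 9.5.1) |
| Injection-site reaction | Yes, local AE tables, plus a listing of other AEs with injection-site terms (SAP 9.5.1) |
| Numeric laboratory and ECG values | Yes, descriptive statistics by visit (SAP 9.5.2, 9.5.5) |
| Normal to abnormal-NCS, transient or persistent | No categorical count |

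**The case against.** The strongest reply is that little is hidden. A reader might infer from the shift tables that near-peak safety findings disappear from the report. The documents do not support that: CS findings become AEs at any post-dose time, and injection-site reactions have their own tables and listing without having to be graded CS. Nor can the SAP hide near-peak ECGs in Cohorts 1 to 3, because none are scheduled.

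The cohorts are also very small. With n = 3, the minimum, median and maximum by visit are the three individual values. With n = 5, adding the quartiles gives all five under SAS's default percentile definition (an assumption; the SAP names none). Since a D-dimer of 0.5 µg/mL or more at screening excludes a patient, the number above that cut-off at 6 h or 24 h can usually be read from the planned table. This largely stands for D-dimer at a single visit. It does not extend to TAT and F1+2, which are not screened. The by-visit rows also do not link a subject's values across visits or to his own baseline, and SAP 9.5.2 specifies no subject-level laboratory listing.

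The protocol names no post-dose time, so choosing end of cohort does not by itself contradict it. That also stands: the merge is the clear departure, while the single time point narrows an open phrase. Hematology, chemistry and urinalysis have no scheduled 6 h or 24 h samples, so the time point costs little there. Finally, decisions to open the next cohort rest on the DSMB and DMC reviews (protocol 9.9), not on these post-lock tables.

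**Conclusion.** The point holds in limited form. SAP 9.5.2, 9.5.5 and 10.2 replace the protocol's normal/abnormal count with Normal/NCS against CS at end of cohort only, and section 5 does not say so. SAP 9.5.3 makes the same merge for physical examination. What is lost is a count of subjects who move from normal to abnormal-NCS. The loss is largest for the coagulation panel, where 89% to 92% of scheduled post-baseline draws, including every 6 h and 24 h draw, cannot enter the shift table.

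Two further inferences should be resisted. The activity fractions of 4.5% to 27% do not say how much of a marker rise would be missed. And it should not be assumed that Normal and NCS are recorded separately throughout: the protocol documents three grades at collection only for ECG.

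The conclusion rests on the SAP text being followed as written. The mock tables are not in the text available for review, so an additional shift table there cannot be excluded. The analysis is descriptive and the remedy is small, so this is a cheap improvement.

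**What to change.** - **Coagulation panel (SAP 9.5.2, 10.2).** Tabulate Normal / Abnormal NCS / Abnormal CS from the pre-dose value of each administration period to the worst post-dose value in that period, stating for each marker which direction is worse. If NCS is not recorded separately, use normal/abnormal by the reference range of the laboratory that ran the sample. Keep the end-of-cohort column. The 2nd hospitalization draw supplies the second-period baseline in Cohorts 1 to 3.
- **TAT, D-dimer and F1+2.** Report change from baseline at 6 h and 24 h where collected.
- **ECG (SAP 9.5.5, 10.2).** Use the three collected classes and include the 24 h and 72 h ECGs of Cohorts 4 and 5.
- **Hematology, chemistry, urinalysis and physical examination (SAP 9.5.2, 9.5.3, 10.2).** Separate Normal from NCS where the CRF or reference ranges allow.
- **SAP section 5.** Declare any departure from protocol 7.2.3.2, 7.2.3.4 and 7.2.3.5 that remains.

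For coagulation and ECG the cost is SAP wording and table shells, since the numeric results and ECG grades are already collected. For the other assessments it depends on what the CRF holds. The downside is that more abnormal shifts will be displayed, some of them incidental.
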